### **15.2.2. Intercurrent Event Handling and Data Imputation for Secondary Immunogenicity Variables**

Missing data will not be replaced. Refer also to PPS in section 5.6 and estimand section 2.4.

### **15.2.3. Analysis of Secondary Immunogenicity Variables**

The secondary immunogenicity endpoints will be analyzed as follows:

Document: \\ieedc-vnasc01\BIOSdata\GSK\H5N8(Flu)\HAB99808\Biostatistics\Documentation\SAP\SAP\SAP v5.0\GSK H5N8-219833\_SAP\_v5.0\_19AUG2024.docx  
Author: PPD Version Number: 5.0  
Version Date: 19AUG2024

Template No.: CS\_TP\_BS016 Revision 7

Reference: CS\_WI\_BS005

Effective Date: 01Nov2021

- GMTs, with 95% CIs, will be calculated for each study intervention group for vaccine-homologous H5N8 HI titer at Day 1, 22, and 6 months post dose 2. Results will be tabulated and presented graphically (in log10 scale). H5N8 HI titer will also be displayed using reverse cumulative distribution curves.
- GMFR from pre-vaccination, will be calculated for each study intervention group for vaccine-homologous H5N8 HI titer at Day 22, and 6 months post dose 2 with 95% CIs.
- The CIs for GMT/GMFR at post-vaccination timepoints will be derived from an ANCOVA model on log-transformed titer. This model will include the dose group effect (i.e., 4 dose groups) as a fixed effect and the log-transformed titer pre-dose 1 (Day 1) as a covariate. For GMT at Dose 1, t-student CI will be used. Results will be tabulated and presented graphically (in log10 scale).
- SP, defined as HI titer  $\geq 1:40$ , will be analyzed by reporting SPR. SPR is defined as the percentage of participants who meet the SP definition and will be reported at Day 1, 22, and 6 months post dose 2, with Clopper-Pearson exact two-sided 95% CIs for each study intervention group.
- SC is defined as meeting vaccine-homologous H5N8 HI titer  $\geq 1:40$  in the serum of participants with visit 1 pre-vaccination titer below 1:10 or as a  $\geq 4$ -fold rise in post-vaccination HI titer with pre-vaccination titer  $\geq 1:10$  and will be analyzed by reporting SCR. SCR is defined as the percentage of participants who meet the SC definition and will be reported at Day 22, Day 43 and 6 months post dose 2, with Clopper-Pearson exact two-sided 95% CIs for each study intervention group. Results will be tabulated and presented graphically.
- For a subset of participants with Microneutralization (MN) titers, the following aggregate variables will be calculated for each study intervention group for vaccine-homologous H5N8 MN neutralization titer.
- GMTs and GMFR, with two-sided 95% CIs, will be calculated for each study intervention group for vaccine-homologous H5N8 MN titer at Day 1, 22, 43, and 6 months post dose 2. Results will be tabulated and presented graphically (in log10 scale).
- H5N8 HI & MN neutralization titer will also be displayed using reverse cumulative curves with all timepoints/groups in the same figure for each assay separately.
- Seropositivity rates will be summarized as the percentage of participants with seropositive results at Days 1, 22, 43, and 6 months post dose 2 (percentage of seropositive participants) with Clopper-Pearson exact two-sided 95% CIs for each study intervention group.
- MN VR will be analyzed as vaccine response rate (VRR). VRR is defined as the percentage of participants who meet the VR criteria and will be reported at Days 22, 43, and 6 months post dose 2 with Clopper-Pearson exact two-sided 95% CIs for each study intervention group. Results will be tabulated and presented graphically.

---

Document: \\ieedc-vnasc01\BIOSdata\GSK\H5N8(Flu)\HAB99808\Biostatistics\Documentation\SAP\SAP\SAP v5.0\GSK H5N8-219833\_SAP\_v5.0\_19AUG2024.docx

Author: PPD

Version Number: 5.0

Version Date: 19AUG2024

Template No.: CS\_TP\_BS016 Revision 7

Reference: CS\_WI\_BS005

Effective Date: 01Nov2021

## **16. SAFETY OUTCOMES**

All outputs for solicited events will be based on the DS. All other safety outcomes will be based on the ES.

There will be no statistical comparisons between the study intervention groups for safety data.

### Primary Safety Endpoints

#### Solicited events

- o Percentage of participants reporting each solicited administration site event (pain, erythema / redness, swelling) with onset within 7-days (i.e., day of vaccination and 6 subsequent days) following each vaccination and overall.
- o Percentage of participants reporting each solicited systemic event (fatigue, fever, headache, muscle ache, joint pain, shivering [chills], sweating, nausea, vomiting, diarrhea, abdominal pain) with onset within 7-days (i.e., day of vaccination and 6 subsequent days) following each vaccination and overall.

#### Laboratory tests

- o Percentage of participants with occurrence of toxicity grade increase in either hematology or biochemistry laboratory tests from baseline to 7 days after each vaccination (change in baseline)
- o Shift table for toxicity grading in hematology or biochemistry laboratory tests from baseline to 7 days to 7 days after each vaccination (change in baseline)

#### Unsolicited events

- o Percentage of participants reporting unsolicited adverse events within 21 days (i.e., day of vaccination and 20 subsequent days) following each vaccination and overall.

#### Medically attended adverse events (MAEs)

- o Percentage of participants reporting MAEs for 21 days (i.e., day of vaccination and 20 subsequent days) after each vaccination, through 6 months post dose 2, and overall.

#### Serious adverse events (SAEs)

- o Percentage of participants reporting SAEs until Day 43 and also 6 months post dose 2 following each vaccination and overall.

---

Document: \\ieedc-vnasc01\BIOSdata\GSK\H5N8(Flu)\HAB99808\Biostatistics\Documentation\SAP\SAP\SAP v5.0\GSK H5N8-219833\_SAP\_v5.0\_19AUG2024.docx

Author: PPD Version Number: 5.0  
Version Date: 19AUG2024

Template No.: CS\_TP\_BS016 Revision 7

Reference: CS\_WI\_BS005

Effective Date: 01Nov2021

Potential immune-mediated disease (pIMDs)

- o Percentage of participants reporting pIMDs until Day 43 and also 6 months post dose 2 following each vaccination and overall.

## 16.1. Adverse Events

Adverse Events (AEs) will be coded using MedDRA central coding dictionary, version 25.1 or higher. Adverse events will be described using frequency and percentage.

Adverse Events will be grouped by SOC, HLT and PT and summarized by study intervention at time of onset of the AE. The summary tables will present the number and percentage of total participants and number of events, by SOC and by PT for each study intervention.

For the summaries of AEs, participants who experience the same AE (in terms of the MedDRA SOC, HLT and PT) more than once will only be counted once for that event in the number of participants but all occurrences of the same event will be counted in the number of events.

Causality, as indicated by the Investigator is classed as “related” and “not related” to Q-Pan H5N8 vaccine. A “related” AE is defined as an AE with a relationship to study intervention. If a participant reports the same AE more than once within that SOC / PT, the AE with the worst-case relationship to study intervention will be used in the corresponding relationship summaries for each study intervention.

See [APPENDIX 2](#) for handling of partial dates for AEs.

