9.3 Analysis Sets

Table 9 Analysis Sets

Analysis Set	Description	Analyses Evaluated
Screened	All participants who were screened for eligibility.	Study Population
Enrolled (ENR)	All participants who were randomized, received study intervention or had immunogenicity blood sample.	Study Population
Exposed Set (ES)	Participants who received a study intervention. Participants will be analyzed according to the study intervention administered at dose 1.	Safety (unsolicited AE, number of participants with changes in laboratory toxicity grading from baseline, SAE, pIMD, MAE)
Diary Set (DS)	Participants who received a study intervention and provided information on solicited AEs. Participants will be analyzed according to the study intervention administered at dose 1.	Solicited AE
Per Protocol Set (PPS)	
All eligible participants who received the 2 doses of study intervention as per protocol, had Day 1 and Day 43 post dose anti-HI immunogenicity results as per blood draw interval at Day 43.
 
In addition, participant data at a specific blood draw visit will be excluded from the PPS when:
 
 • Results from a serological blood sample deviated from blood draw intervals (refer to Table 2) • Results from a serological blood sample occurred after intercurrent conditions that may interfere with immunogenicity (i.e., immunosuppressive, immunodeficient conditions, or malignancy) or after a prohibited concomitant medication/vaccination 
The analysis will be done according to the treatment that participants received at Visit 1.
	
Efficacy
 
The PPS will be used for the immunogenicity analyses.

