Primary	The study intervention will be defined by the first dose administered	DS	Solicited administration site events within 7 days after each vaccine administration	1. Paper diary not completed on each day	1. Missing data won't be imputed. Compliance to paper diary will be captured	Percentage and exact 95% CIs of participants with solicited administration site events within 7 days after each vaccine administration.
Primary	The study intervention will be defined by the first dose administered	DS	Solicited systemic event within 7 days after each vaccine administration	1. Paper diary not completed on each day	1. Missing data won't be imputed. Compliance to paper diary will be captured	Percentage and exact 95% CIs of participants with solicited systemic events within 7 days after each vaccine administration.
Primary	The study intervention will be defined by the first dose administered	ES	Each toxicity grade change from baseline in hematology or biochemistry laboratory tests 7 days after each vaccine administration	1. Permanently discontinued from study due to any reasons prior to Day 7	1. Missing data won't be imputed. Summaries will present the actual data	Percentage and exact 95% CIs of participants with toxicity grade change from baseline for hematology or biochemistry laboratory

Document: \\ieedc-vnasc01\BIOSdata\GSK\H5N8(Flu)\HAB99808\Biostatistics\Documentation\SAP\SAP\SAP v5.0\GSK H5N8-219833\_SAP\_v5.0\_19AUG2024.docx

Author: PPD Version Number: 5.0  
Version Date: 19AUG2024

Template No.: CS\_TP\_BS016 Revision 7 Reference: CS\_WI\_BS005

Effective Date: 01Nov2021

	Study Intervention	Analysis set	Variable (or endpoint)	Intercurrent events (ICEs)		Population level summary
				Description	Handling strategy	
						tests 7 days after each vaccine administration
Primary	The study intervention will be defined by the first dose administered	ES	Each unsolicited adverse event within 21 days after each vaccine administration	1. Permanently discontinued from study due to any reasons prior to Day 21	1. Missing data won't be imputed. Summaries will present the actual data	Percentage and exact 95% CIs of participants with unsolicited adverse events within 21 days after each vaccine administration.

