### **5.4. Exposed Set [ES]**

Participants who received a study intervention. For analyses and displays based on ES, participants will be classified according to study intervention administered at dose 1 (i.e., study intervention actually received).

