### **5.5. Diary Set [DS]**

Participants who received a study intervention and provided information (at least one AE for at least one day) on any solicited AE. For analyses and displays based on DS, participants will be classified according to study intervention administered at dose 1 (i.e., study intervention actually received). Participants to have at least one day of complete diary data to be included in DS.

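### SAP 16.1 groups coded AEs by the intervention at onset, but the safety denominators follow dose 1; the two rules part if a participant is given a different formulation at dose 2 by error

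*SAP*

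**What the plan says.** SAP 16.1 (Adverse Events) states that AEs are grouped by SOC, HLT and PT and "summarized by study intervention at time of onset of the AE". It continues: "The summary tables will present the number and percentage of total participants and number of events", by SOC and PT for each study intervention.

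SAP 16 bases every safety output other than solicited events on the Exposed Set (ES). SAP 5.4 fixes the grouping for that set: "For analyses and displays based on ES, participants will be classified according to study intervention administered at dose 1". SAP 5.5 gives the same rule for the Diary Set (DS). Protocol 9.3, Table 9, agrees for both sets: "Participants will be analyzed according to the study intervention administered at dose 1". Each safety row of SAP 2.4 repeats it: "The study intervention will be defined by the first dose administered".

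SAP 16.1.2 tabulates unsolicited AEs after each vaccination and overall, as numbers and percentages with exact 95% CIs. SAP 16.1.4 and 16.1.5 plan exact CIs for SAEs and pIMDs. SAP 3.3 declares no changes from the protocol.

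**The concern.** One rule decides the group in which an AE is counted, and another decides the group in which the participant is counted. In a parallel-group trial the two coincide unless someone is given one formulation at dose 1 and another at dose 2. Such a participant stays in the ES, because that set asks only that a study intervention was received.

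For that participant, 16.1 taken literally puts AEs with onset after dose 2 in the group of the second formulation, while ES membership stays with the first. The numerator then holds someone who is not in the denominator. A Clopper-Pearson interval assumes that the numerator counts members of N, so it has no valid meaning there. With small cells and rare events, the choice of rule can also decide which group displays an SAE or pIMD. That choice should be fixed before unblinding.

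**Working it through.** The plan states no figure on this point to reproduce. The check compares the rules and then sizes the mismatch.

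**Inputs**
- AE grouping: intervention at onset (SAP 16.1).
- Participant grouping: dose 1 (SAP 5.4, 5.5 and 2.4; Protocol Table 9).
- Set for unsolicited AEs, MAEs, SAEs and pIMDs: ES (SAP 16).
- Planned cell size: 65 per age subgroup in each dose group (SAP 2.5). SAP 6 reports the age groups separately.
- k, the number of participants in a cell with a different formulation at dose 2 and a qualifying AE after it. The documents give no count, so k is an assumption.

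**Step 1: one participant under both rules.** Take a participant given 750_A at dose 1 and, by error, 375_A at dose 2. The participant belongs to the 750_A denominator throughout.

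| Row | Dose 1 rule | SAP 16.1 read literally |
|---|---|---|
| AE after dose 1 | 750_A | 750_A (no conflict) |
| AE after dose 2 | 750_A | 375_A, where N excludes the participant |
| Overall, AE only after dose 2 | 750_A | 375_A, where N excludes the participant |
| Overall, qualifying AE after both doses | 750_A, once | 750_A and also 375_A |

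In the last row nothing leaves the dose 1 group, but the other group still gains a participant outside its N. The conflict is most direct in the post-dose-2 rows, where every AE of that participant is reassigned.

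**Step 2: size per participant.** The shift is k/N in each of the two cells, except that the dose 1 cell loses nothing in the last row above.
- k = 1: 1/65 = 1.54 points.
- k = 2: 2/65 = 3.08 points.
- k = 3: 3/65 = 4.62 points.
- k = 5: 5/65 = 7.69 points.
- k = 0: no change.

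**Step 3: illustration.** Assume 13/65 = 20.0% in both cells under the dose 1 rule, and k = 1 in a post-dose-2 row.
- Dose 1 cell: (13 − 1)/65 = 12/65 = 18.5%, nominal exact 95% CI 9.9% to 30.0%.
- Other cell: (13 + 1)/65 = 14/65 = 21.5%, nominal exact 95% CI 12.3% to 33.5%.

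For a single SAE after dose 2, the rule decides which cell shows 1/65 (CI 0.04% to 8.3%) and which shows 0/65 (CI 0% to 5.5%).

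**Step 4: after the fix.** With dose 1 used for both numerator and denominator, the mismatch is zero by construction. Sample size, power and type I error do not change.

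**The case against.** The strongest reply is that the phrase is only loose wording. The SAP sometimes uses study intervention to mean a dose (SAP 6.2 and 12). SAP 6.1 dates AE start from the last vaccination, and SAP 16.1.2 tabulates by vaccination. On that reading, 16.1 means the dose preceding onset, and there is no conflict. This reading is possible, but it fits the rest of 16.1 poorly: the next sentence presents results for each study intervention, which reads as a group. If the group is always the dose 1 group, the words about onset add nothing.

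Grouping by the formulation most recently received could also be defended on its merits, but it would need matching denominators, and the plan defines none.

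A reader might infer more than the documents support:
- **That no rule governs.** SAP 16 with 5.4 and 5.5 points to dose 1, and the statement of no changes in SAP 3.3 supports the protocol's rule. The defect is that 16.1 contradicts it.
- **That formulation switches are expected.** Protocol Table 1 allocates study group and treatment number at Visit 1, and only a treatment number at Visit 3. Incorrect vaccination in Protocol 9.3.1 is a general deviation category. No switch is reported.
- **That all primary safety endpoints are affected.** The 16.1 sentence concerns coded AEs. For solicited events, "All outputs for solicited events will be based on the DS", by individual symptom, and laboratory grade increases fall under SAP 16.2. The sentence does not clearly reach either.
- **That whole-study lines suffer most, or that 1/65 always leaves the dose 1 group.** Step 1 shows otherwise.
- **That a formal comparison of formulations is compromised.** SAP 16 plans no statistical comparison between groups for safety.

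**Conclusion.** The phrase in SAP 16.1 is wrong as written, and the severity is low. It conflicts with the dose 1 classification used elsewhere in the SAP and in the protocol. Followed literally, it would give invalid percentages and exact CIs for coded AEs in the two cells concerned.

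The size is up to 1/65 = 1.5 points per affected participant in an age-by-dose cell, mainly in the post-dose-2 rows. This assumes the planned cell size, a different formulation given at dose 2 by error, and a qualifying AE with onset after it. If no such error occurs, no result changes. The immunogenicity hypotheses are not touched.

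**What to change.** In SAP 16.1, replace the phrase with: *summarized by the study intervention administered at dose 1 (ES definition), and by the vaccination after which the AE started*. This keeps the timing information and puts numerator and denominator on one rule.

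In the deviation listing (SAP 9.2) and the AE, SAE and pIMD listings (SAP 16.1.2, 16.1.4 and 16.1.5), flag any participant whose dose 2 formulation differed from dose 1, so that events after the other formulation stay visible. No new listing is needed.

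The cost is one phrase in the SAP and one flag in outputs already planned.

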### 16.1.1. Solicited Adverse Events

Solicited administration site events and solicited systemic events to be summarized are included in [Table E](#). Intensity scales for solicited events (administration site and systemic) are included in [Table F](#) and [Table G](#).

Table E: Solicited events

Solicited administration site events	Solicited systemic events
--------------------------------------	---------------------------

Document: \\ieedc-vnasc01\BIOSdata\GSK\H5N8(Flu)\HAB99808\Biostatistics\Documentation\SAP\SAP\SAP\SAP v5.0\GSK H5N8-219833\_SAP\_v5.0\_19AUG2024.docx

Author: PPD Version Number: 5.0

Version Date: 19AUG2024

Template No.: CS\_TP\_BS016 Revision 7

Reference: CS\_WI\_BS005

Effective Date: 01Nov2021

Pain at Injection Site	Fever
Erythema / Redness at Injection Site	Headache
Swelling at Injection Site	Fatigue
	Muscle ache
	Joint pain
	Shivering (chills)
	Sweating
	Nausea
	Vomiting
	Diarrhea
	Abdominal pain

Table F: Intensity scales for solicited events in adults 18 years of age or older

Adults ( $\geq 18$ years)		
Event	Intensity grade	Parameter
Pain at administration site	0	None
	1	Mild: Any pain neither interfering with nor preventing normal everyday activities.
	2	Moderate: Painful when limb is moved and interferes with everyday activities.
	3	Severe: Significant pain at rest. Prevents normal everyday activities.
Headache	0	Normal
	1	Mild: Headache that is easily tolerated.
	2	Moderate: Headache that interferes with normal activity.
	3	Severe: Headache that prevents normal activity.
Fatigue	0	Normal
	1	Mild: Fatigue that is easily tolerated.

Document: \\ieedc-vnasc01\BIOSdata\GSK\H5N8(Flu)\HAB99808\Biostatistics\Documentation\SAP\SAP\SAP v5.0\GSK H5N8-219833\_SAP\_v5.0\_19AUG2024.docx

Author: PPD

Version Number: 5.0

Version Date: 19AUG2024

Template No.: CS\_TP\_BS016 Revision 7

Reference: CS\_WI\_BS005

Effective Date: 01Nov2021

Adults (≥18 years)		
Event	Intensity grade	Parameter
	2	Moderate: Fatigue that interferes with normal activity.
	3	Severe: Fatigue that prevents normal activity.
Muscle ache all over body	0	Normal
	1	Mild: Muscle aches that are easily tolerated.
	2	Moderate: Muscle aches that interfere with normal activity.
	3	Severe: Muscle aches that prevent normal activity.
Joint pain	0	Normal
	1	Mild: Joint pain that is easily tolerated.
	2	Moderate: Joint pain that interferes with normal activity.
	3	Severe: Joint pain that prevents normal activity.
Shivering (chills)	0	Normal
	1	Mild: Shivering (chills) that is easily tolerated.
	2	Moderate: Shivering (chills) that interferes with normal activity.
	3	Severe: Shivering (chills) that prevents normal activity.
Sweating	0	Normal
	1	Mild: Sweating that is easily tolerated.
	2	Moderate: Sweating that interferes with normal activity.
	3	Severe: Sweating that prevents normal activity.
Gastrointestinal symptoms: nausea, vomiting, diarrhea and/or abdominal pain	0	Normal
	1	Mild: Gastrointestinal symptoms that are easily tolerated.
	2	Moderate: Gastrointestinal symptoms that interfere with normal activity.
	3	Severe: Gastrointestinal symptoms that prevent normal activity.
Redness at administration site		Record greatest surface diameter in mm

Document: \\ieedc-vnasc01\BIOSdata\GSK\H5N8(Flu)\HAB99808\Biostatistics\Documentation\SAP\SAP\SAP v5.0\GSK H5N8-219833\_SAP\_v5.0\_19AUG2024.docx

Author: PPD

Version Number: 5.0

Version Date: 19AUG2024

Template No.: CS\_TP\_BS016 Revision 7

Reference: CS\_WI\_BS005

Effective Date: 01Nov2021

Adults (<math>\geq 18</math> years)		
Event	Intensity grade	Parameter
Swelling at administration site		Record greatest surface diameter in mm
Temperature		Record temperature in $^{\circ}\text{C}/^{\circ}\text{F}$ . Oral route is preferred.

Table G: Intensity scales for solicited events – erythema / swelling and fever

	Erythema/swelling	Fever (Temp <math>^{\circ}\text{C}</math>)
0:	$\leq 20$ mm	$<38.0$ $^{\circ}\text{C}$ $(<100.4$ $^{\circ}\text{F})$
1:	$> 20 - \leq 50$ mm	$\geq 38.0$ $^{\circ}\text{C}$ ( $100.4$ $^{\circ}\text{F}$ ) - $\leq 38.4$ $^{\circ}\text{C}$ ( $101.2$ $^{\circ}\text{F}$ )
2:	$> 50 - \leq 100$ mm	$\geq 38.5$ $^{\circ}\text{C}$ ( $101.3$ $^{\circ}\text{F}$ ) - $\leq 38.9$ $^{\circ}\text{C}$ ( $102.1$ $^{\circ}\text{F}$ )
3:	$> 100$ mm	$\geq 39.0$ $^{\circ}\text{C}$ ( $102.2$ $^{\circ}\text{F}$ ) - $\leq 40.0$ $^{\circ}\text{C}$ ( $104.0$ $^{\circ}\text{F}$ )
4:		$>40.0$ $^{\circ}\text{C}$ ( $104.0$ $^{\circ}\text{F}$ )

Solicited events will be summarized and listed as:

- The number and percentage of participants, with exact 95% CIs, reporting each individual solicited administration site AE (pain, erythema/swelling, swelling) for all grades, grade  $\geq 2$ , grade  $\geq 3$ , medically attended events during the 7-day follow-up period, and ongoing at the end of the 7-day follow-up period will be tabulated following each vaccination and overall.
- The number and percentage of participants, with exact 95% CIs, reporting each individual solicited systemic AE (fatigue, fever, headache, muscle ache, joint pain, shivering [chills], sweating, gastrointestinal symptoms [nausea, vomiting, diarrhea, abdominal pain]) for all grades, grade  $\geq 2$ , grade  $\geq 3$ , medically attended events during the 7-day follow-up period, and ongoing at the end of the 7-day follow-up period will be tabulated following each vaccination and overall.
- The number and percentage of participants, with exact 95% CIs, reporting any solicited administration site AE, any solicited systemic AE and any solicited AE (across all administration site and systemic symptoms), for all grades, grade  $\geq 2$ , grade  $\geq 3$ , medically attended events during the 7-day follow-up period will be tabulated following each vaccination and overall.

Document: \\ieedc-vnasc01\BIOSdata\GSK\H5N8(Flu)\HAB99808\Biostatistics\Documentation\SAP\SAP\SAP v5.0\GSK H5N8-219833\_SAP\_v5.0\_19AUG2024.docx

Author: PPD

Version Number: 5.0

Version Date: 19AUG2024

Template No.: CS\_TP\_BS016 Revision 7

Reference: CS\_WI\_BS005

Effective Date: 01Nov2021

- Duration of solicited events reported during the 7-day follow-up period will be tabulated for each individual solicited event using descriptive statistics (mean, minimum, Q1, median, Q3, maximum).. The start date is the first during the 7-day solicitation period with the symptom at grade > 0 while the stop date is the last day with the symptom at grade > 0 in or beyond the solicited period. In addition, the duration for specific grade(s) (grade  $\geq$  2, grade  $\geq$  3 and medically attended solicited events) for each symptom defined as the number of days in the reporting period with grade above or equal to specific grade will be summarized.
- All solicited administration site events will be included in a listing. Prolonged solicited AEs that continue beyond the 7-day follow-up period will be identified using a flag in the listing of solicited administration site events.
- All solicited systemic events will be included in a listing. Prolonged solicited AEs that continue beyond the 7-day follow-up period will be identified using a flag in the listing of solicited systemic events.

